6.2.6.1. Estimated Glomerular Filtration Rate (eGFR)

Serum creatinine will be measured every 8 months by a central laboratory. It will be used to calculate eGFR using the MDRD formula [Levey, 2009], namely:

$$\text{eGFR (ml/min/1.73m}^2\text{)} = 175 \times (\text{serum creatinine})^{-1.154} \times (\text{Age})^{-0.203} \times (0.742 \text{ if female}) \times (1.212 \text{ if African American}).$$

6.2.7. Physical examination

A general physical examination, including height and neck (thyroid), will be performed at randomization. A targeted physical examination will be performed at all other time points as specified in the Time and Events Table (Table 1). The targeted physical examination will evaluate the cardiovascular system and injection sites and will include measurement of blood pressure and heart rate taken with the subject either in a semi-recumbent or seated position after at least a 5-minute rest period.

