| Physical examination ^{9,11} | | X | | X (alternate visits) 2 | | X | X | |
| SAEs, AEs of special interest, AEs leading to IP discontinuation | | X | X | X | X | X | X | X |
| Pregnancy test ^{10,12} | X | X | | | | | | |
| Study drug dispense/compliance ^{11,13} | | X | | X | X | X | X | |

- Subjects who discontinue investigational product should be handled as described in Section 4.4 and Section 4.5 **and in Table 2.**
- ~~Assessments per the Month 4 visit will alternate with those per the Month 8 visit throughout the study i.e., assessments at months 4, 12, 20 etc will be per Month 4; those at month 8, 16, 24 etc. will be per Month 8.~~ **Assessments at month 8, 16, 24 etc. will include patient reported outcomes questionnaires, serum creatinine (eGFR), liver function tests and physical examination. Those at months 4, 12, 20 etc do not.**
- Screening and Randomisation can occur at the same visit if all eligibility information is available. If Screening and Randomisation occur at the same visit assessments should not be duplicated.
- Once it is projected that the target number of MACE events will have been collected, a 3 month window will be defined for conducting the final, face to face visit.
- HbA1c and creatinine assessed using local laboratories at Screening visit and measured no more than 6 months prior to randomisation. If HbA1c or creatinine have not been assessed in the previous 6 months assessments to be performed via a central laboratory and results available prior to randomization. The investigator has the discretion to repeat screening HbA1c, and/or creatinine, based on clinical rationale even if previously available local results meet the eligibility criteria to allow the investigator to accommodate the possibility of change between screening and randomisation.
- Liver function tests: ALT, AST, alkaline phosphatase, bilirubin, GGT. Blood samples for LFTs at randomization must be collected prior to the first dose of investigational product.
- Lipid values (TC, LDLc, HDLc, Tg) to be recorded as available from routine clinical care at baseline and annually thereafter. If results are unavailable, lipid tests are not to be performed for the study.**
- Informed consent for genetic research must be obtained before collecting a sample. ~~Genetics sample~~ **This** can be collected at any time after genetic consent has been obtained and ~~the subject has been randomised~~ **randomisation has occurred.**

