2. OBJECTIVES AND ENDPOINTS

| Objectives | Endpoints |
|--|---|
| Primary | |
| To determine whether albiglutide is non-inferior with respect to MACE when added to glycaemic standard of care versus standard of care alone | 
 Time to first occurrence of MACE (cardiovascular death, myocardial infarction, or stroke) [Non-inferiority] |
| Secondary | |
| To supplement the primary objective by further characterization of the effects of albiglutide on cardiovascular outcomes | 
 Time to first occurrence of MACE [Superiority]^(1 see footnote) Time to first occurrence of the following: 
 MACE or urgent revascularisation for unstable angina The individual components of the primary endpoint Cardiovascular death or hospitalization due to heart failure |
| To evaluate the effects of albiglutide on metabolic management of type 2 diabetes | 
 Time to initiation of insulin of more than 3 months duration for those subjects not treated with insulin at study start ^(1 see footnote) Time to initiation of prandial insulin in those subjects on basal insulin at study start The proportion of subjects achieving glycaemic control (HbA1c ≤ 7.0% at final assessment) with no severe hypoglycaemic incidents and weight gain <5% of body weight ^(1 see footnote) The time to first occurrence of a clinically important microvascular event (see Section 6.2.4) Change in HbA1c Change in body weight Patient reported outcomes from TRIM-D/EQ5D |
| To evaluate the safety of albiglutide | 
 All cause mortality Non-fatal SAEs AEs leading to discontinuation of investigational product AE of special interest (see Section 6.2.3) Change in eGFR calculated using MDRD formula Change in blood pressure and heart rate |
| Exploratory | |
| To evaluate patient reported experience of diabetes treatment | 
 Patient reported outcomes from study specific questionnaire |

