8.3.5. Multiplicity Controls

A multiple comparisons adjustment strategy will be implemented for the multiple inferential tests among the primary endpoint and secondary endpoints of MACE superiority, time to insulin and composite metabolic endpoint.

The strategy will use a combination of gatekeeper and Hommel procedure. The first step is to evaluate the MACE non-inferiority of the albiglutide group vs the placebo group at a one-sided $\alpha=0.025$ level. If the result of non-inferiority is significant, MACE superiority, time-to-insulin and composite metabolic endpoint will be tested simultaneously using the Hommel procedure with $\alpha=0.05$. The above multiplicity control approach will preserve the study's nominal significance level of 0.05. The test order is illustrated in the diagram below.

Hommel Procedure for secondary endpoints is described below:

Three hypothesis tests for MACE superiority, time-to-insulin, and composite metabolic endpoint are subject to be adjusted by the Hommel procedure. Let $P(1)$, $P(2)$ and $P(3)$ represent the ordered p-values that $P(3) > P(2) > P(1)$ and $H(1)$, $H(2)$ and $H(3)$ are corresponding hypotheses.

If $P(3) < 0.05$, reject $H(3)$, $H(2)$, $H(1)$. End of test.

If $P(3) \geq 0.05$ and $P(2) < 0.05/2$, accept $H(3)$, reject $H(2)$, $H(1)$. End of test.

If $P(3) \geq 0.05$ and $P(2) \geq 0.05/2$ and $P(1) < 0.05/3$, accept $H(3)$, $H(2)$, reject $H(1)$. End of test.

If $P(3) \geq 0.05$, $P(1) \geq 0.05/3$ and $0.05/2 \leq P(2) < 0.05 \cdot 2/3$, accept $H(3)$, $H(2)$, reject $H(1)$. End of test.

If $P(3) \geq 0.05$, $P(2) \geq 0.05 \cdot 2/3$ and $P(1) \geq 0.05/3$, accept $H(3)$, $H(2)$ and $H(1)$.

Other Secondary Endpoints and Subgroup Analysis

The following secondary endpoints will provide supportive evidence for cardiovascular safety and will not use any multiplicity adjustment procedure.

- Components of primary endpoint (MACE = cardiovascular death, MI, stroke)
- MACE + urgent revascularisation for unstable angina
- Cardiovascular death or hospitalisation for heart failure

Other secondary endpoints which do not qualify for formal statistical hypothesis testing will be analyzed and have results presented with confidence interval and nominal p-values:

- Mean HbA1c at scheduled visits and change from baseline
- Mean body weight at scheduled visits and change from baseline
- Mean eGFR at scheduled visits and change from baseline
- Time to initiation of prandial insulin

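### Body weight is a secondary endpoint and a component of the alpha-controlled metabolic composite, but the protocol's schedule and examination lists provide for no follow-up or final weight

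*Protocol*

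**What the plan says.** **What the analysis requires.** Section 2 lists "Change in body weight" among the secondary endpoints. It also defines a composite of HbA1c control "with no severe hypoglycaemic incidents and weight gain <5% of body weight". Section 8.3.6.2 joins the three conditions by AND, evaluates them at the end of the study and adds supplementary results by scheduled visit. Section 8.3.5 gives the composite confirmatory status: once non-inferiority is shown, "MACE superiority, time-to-insulin and composite metabolic endpoint will be tested simultaneously using the Hommel procedure". The same section lists "Mean body weight at scheduled visits and change from baseline" for reporting with nominal p-values, and Section 8.3.6.2 fits a repeated mixed model to weight. Section 8.3.3 plans a baseline summary that includes weight and BMI.

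**What the schedule provides.** The Table 1 row for physical examination refers to Section 6.2.7 for its content. There, "A general physical examination, including height and neck (thyroid), will be performed at randomization". For every later time point, "The targeted physical examination will evaluate the cardiovascular system and injection sites and will include measurement of blood pressure and heart rate". Weight is named in neither. Table 1 has no row for it, Section 6.2.6 covers laboratory tests only, and the tables printed in the Amendment 2 change list add a row for lipids but none for weight.

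**The concern.** When a weight is taken is protocol content. An analysis plan can say how to use weights, but it cannot create measurements that the schedule did not call for. Section 3.1 describes a trial with little intervention beyond usual care and makes adherence to Table 1 mandatory. A site that follows Table 1 and Section 6.2.7 to the letter would have no instruction to weigh anyone after randomisation.

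Two things are at stake. The first is the composite, one of only three secondary hypotheses with multiplicity control. The second is the weight endpoint with its longitudinal model. A final weight that was not taken cannot be recovered afterwards.

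**Working it through.** The plan gives no figure for this point, so the check sets the needs of the analysis against the schedule. The protocol's one sample-size figure does reproduce: 4 × (1.960 + 1.282)² / (ln 1.3)² = 4 × 10.51 / 0.0688 ≈ 611 events. Weight does not enter it.

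**Step 1. Trace each measured quantity to its place in the schedule.**

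| Quantity the analysis uses | Where it is collected |
|---|---|
| HbA1c | Own row in Table 1: screening, each 4-monthly clinic visit, final visit |
| Severe hypoglycaemia | Row for adverse events of special interest, at every contact from randomisation on; defined in Section 6.2.3 |
| eGFR | Serum creatinine row: screening, 8-month visits, final visit; Section 6.2.6.1 |
| Blood pressure, heart rate | Physical examination row; both named in Section 6.2.7, with posture and rest period |
| Height | Named in Section 6.2.7, at randomisation |
| Body weight | No row in any table; not named in Section 6.2.6 or 6.2.7 |

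Weight is the only quantity in this list with no source.

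**Step 2. Count.** Weight measurements expressly scheduled: 0 at baseline, 0 at follow-up visits, 0 at the final visit. The condition "weight gain <5% of body weight" compares a final with a baseline value, so it needs at least two weights per subject. The mixed model needs repeated weights after baseline as well.

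**Step 3. What can be inferred at baseline.** The word including in the description of the randomisation examination leaves its list open. Section 8.3.3 plans to summarise baseline weight and BMI, and Section 8.3.6.3 names BMI as a possible subgroup. A baseline weight is therefore presupposed, though not scheduled.

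**Step 4. Follow-up and final visit.** The same inference does not carry over. Section 6.2.7 describes the targeted examination by its content, down to the rest period before blood pressure, and weight is absent. No baseline-type summary implies that a later weight is taken; only the endpoints themselves do.

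**Step 5. Effect on the composite.** The conditions are joined by AND. A subject who misses the HbA1c target or has a severe hypoglycaemic incident is a non-responder whatever the weight. A subject who meets both other conditions cannot be classified without a weight. Every success therefore depends on the unscheduled measurement.

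**Step 6. Status of the text.** The wording of Section 6.2.7 read here is that of Amendment 1. The main body of Amendment 2 was not available. Its itemised change list shows no edit to Section 6.2.7, and its amended Table 1 and new table for subjects who permanently stop drug have no weight row. That the omission carries over is inferred from this.

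**The case against.** The strongest reply is that weight is surely collected. Section 6 sends detailed procedures to the Study Reference Manual, data go into sponsor-defined case report forms, and neither is shown. This stands against any claim that the data do not exist. It does not answer the point about the protocol: Section 3.1 reserves the manual for information that need not be in the protocol, and the timing of a confirmatory endpoint's component is not of that kind.

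Three stronger readings are tempting, and the documents do not support them.

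- *The endpoints have no data.* A reader might infer this from the empty schedule. The text shows silence on follow-up weight, not absence of collection, and at baseline it presupposes a weight. That practice would vary from site to site is likewise conjecture.
- *By-visit composites at months 4, 12 and 20 are impossible.* Of the visits in those months, Amendment 2 says that they leave out the physical examination: "Those at months 4, 12, 20 etc do not". But Section 8.3.5 also promises eGFR at scheduled visits, and creatinine is measured only every 8 months. The phrase can therefore mean visits at which the variable is scheduled. These by-visit results also carry nominal p-values only.
- *An unevaluable composite tightens the other two Hommel tests by a known amount.* The protocol does not say how a hypothesis without a p-value enters the procedure, so no threshold follows.

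It is also fair to say that the primary objective is untouched: neither the MACE non-inferiority test nor the gatekeeping step uses weight.

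**Conclusion.** The protocol contradicts itself between endpoints and assessments. One named secondary endpoint, and one of the three components of one of the three Hommel-tested hypotheses, rest on a measurement that the schedule does not prescribe after randomisation and only presupposes at baseline. One of three here counts components, not a share of alpha. From the schedule as written, the composite and the longitudinal weight analysis cannot be computed.

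The conclusion rests on two assumptions: that Section 6.2.7 passed unchanged into Amendment 2, as its change list suggests, and that the protocol itself, not an operational manual, must state when endpoint data are taken. Because the primary analysis is unaffected and weight may be collected under documents not shown, this is a should-fix point.

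**What to change.** Name body weight in Section 6.2.7 for both the general and the targeted examination. Give it its own row in Table 1 and in the clinic-visit columns of the table for subjects who permanently discontinue investigational product. The time points are randomisation, the 8-month clinic visits, the drug-discontinuation visit and the final visit. In Section 8.3.6.2, state that the by-visit composite is reported for visits at which weight is taken.

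The cost is one row in each table, a sentence in each of two sections and a scale reading at visits already held. If the case report form already captures weight at these visits, the change only brings the protocol into line with practice.

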6.3. Value Evidence and Outcomes

6.3.1. Value Evidence and Outcomes Assessments

6.3.1.1. Treatment Related Impact Measure – Diabetes (TRIM-D)

In order to evaluate satisfaction with treatment and to compare satisfaction across treatment groups, the TRIM-D questionnaire will be self administered by all subjects at baseline and at each 8 month visit (and, to the extent possible, at the time of study completion or withdrawal from the study).

The TRIM-D, developed in 2009, is a 28-item treatment satisfaction measure scored to produce 5 sub-scale scores (Treatment Burden, Daily Life, Diabetes Management,

Psychological Health, and Compliance) as well as a total score. It is available in a wide range of translations.

The TRIM-D development, in accordance with the principles of the Food and Drug Administration Patient Reported Outcome Guidance document, was based on findings from the published literature including content from already-existing treatment satisfaction measures as well as significant input from subjects with type 1 and with type 2 diabetes and from expert diabetes clinicians. The TRIM-D has been evaluated in a sample of 507 subjects (74% with type 2 diabetes) and has been shown to have acceptable reliability and validity [Brod, 2009a]. Its responsiveness was also evaluated in a sample of 242 subjects (71% with type 2 diabetes) and found to be acceptable [Brod, 2009b]. Some preliminary work has been done on estimating its minimal important difference but this needs further exploration [Brod, 2009b].

6.3.1.2. EQ-5D

The EQ-5D will be self-administered by subjects in order to measure generic health status. Combining the EQ-5D with the disease-specific TRIM-D, which is designed to have maximum sensitivity to relevant aspects of disease related treatment, will provide a more robust evaluation of the impact of treatments for type 2 diabetes and allow for clearer interpretation of study results. TRIM-D results, if consistent with the general trends seen in the EQ-5D, will have enhanced credibility.

The EQ-5D is a standardized instrument used to evaluate generic health-related quality of life. It is applicable to a wide range of health conditions and treatments, and it provides a simple descriptive profile and a single index value for health status. It is also used to provide utilities, or preference weights, for use in economic (cost effectiveness) evaluations. It is available in 141 self complete official language versions.

The EQ-5D has been used extensively in studies to measure the impact of type 2 diabetes and treatments for the disease. A systematic review identified 54 publications reporting EQ-5D responses and 39 papers presenting evidence on the measurement properties of the EQ-5D in this population [Janssen, 2011]. This evidence supported the validity, reliability, and responsiveness of the EQ-5D for evaluating health-related quality of life in subjects with type 2 diabetes. Other studies reported that index scores from the EQ-5D have been shown to be an independent predictor of the risk of mortality, future vascular events, and other complications in people with type 2 diabetes [Clarke, 2009]. In addition, the SHIELD longitudinal study (1,741 respondents with type 2 diabetes and 4,543 without diabetes) used the EQ-5D to assess the 5-year changes in health-related quality of life in type 2 diabetes [Grandy, 2012].

6.3.1.3. Exploratory Diabetes Management Questions

In addition to the standardised instruments described above, patient experience in relation to the management of their diabetes will be evaluated in a subset of sites using a small number of self-administered diabetes management questions. These types of customized questions have been used successfully in asthma and in diabetes when patients are involved with goal-setting [Juniper, 1992; Anderson, 2010]. This tailored approach is an

opportunity to capture data in the study that are not otherwise available from standard PRO measures such as the TRIM-D and the EQ-5D. As an exploratory endpoint, this set of questions (3 items at baseline, and at each 8 month follow-up visit) imposes very little patient or site burden, but can offer critical insight into the one area of the patient's choosing that s/he finds most difficult to manage. In addition, this patient-centred endpoint has the potential to be sensitive to changes over time.

These questions have been developed by GSK based on factors identified as important to subjects in the development of published, validated and reliable subject reported outcomes instruments in type 2 diabetes.

6.3.1.4. Healthcare Resource Utilisation

Data will be collected on the following healthcare resource use:

- All cause hospitalisations and related healthcare resource use.

Healthcare resource use data will be collected in order to facilitate subsequent health-economic analyses comparing costs between albiglutide added to standard of care and placebo added to standard of care (cost is not an end point in the study).

Data on all-cause hospitalizations and related inpatient healthcare resource use will be collected. This will include:

- All-Cause hospitalisation including: Admission and discharge diagnoses (primary and secondary), length of stay, level/type of ward, and time spent in Intensive Therapy Unit (or equivalent).

6.4. Genetic Research

Information regarding genetic research is included in [Appendix 1](#).

7. DATA MANAGEMENT

- For this study subject data will be entered into GSK defined eCRFs, transmitted electronically to GSK or designee and combined with data provided from other sources in a validated data system.
- Management of clinical data will be performed in accordance with applicable GSK standards and data cleaning procedures to ensure the integrity of the data, e.g., removing errors and inconsistencies in the data.
- Adverse events and concomitant medications terms will be coded using MedDRA (Medical Dictionary for Regulatory Activities) and an internal validated medication dictionary, GSKDrug.
- CRFs (including queries and audit trails) will be retained by GSK, and copies will be sent to the investigator to maintain as the investigator copy. Subject initials will not be collected or transmitted to GSK according to GSK policy.

8. DATA ANALYSIS AND STATISTICAL CONSIDERATIONS

8.1. Hypotheses

This trial will examine the following primary question:

- Whether albiglutide is non inferior by a margin of 1.3 with respect to its effect on adjudicated MACE, when added to glycaemic standard of care, versus standard of care alone. Letting λ_1 = hazard ratio for time to first MACE for albiglutide vs placebo, then:

Null hypothesis: $\log \lambda_1 \geq \log(1.3)$

Alternative hypothesis: $\log \lambda_1 < \log(1.3)$

8.2. Study Design Considerations

8.2.1. Sample Size Assumptions

The primary outcome will be analyzed such that the overall Type 1 error is no greater than 5% (two-sided). Specifically, the non-inferiority assessment of albiglutide compared to placebo will be conducted at 0.05 level, requiring one-sided significance at 0.025.

The power for MACE non-inferiority is calculated via the asymptotic variance and normality of the maximum likelihood estimator for the log-hazard ratio. Assuming a true hazard ratio of 1.0, 611 events will be needed to have 90% power to rule out non-inferiority margin of 1.3 for the hazard ratio with type I error of 0.05. The study duration will be event-driven. A total of 9400 subjects will be enrolled and followed until it is projected that approximately 611 adjudicated MACE events will have occurred. If the observed rate for MACE is 2.0% or 3.0%, the mean follow-up will be 3.2 or 2.2 years respectively, assuming that the number of subjects lost to follow-up accounts for 1% or less.

8.2.2. Sample Size Sensitivity for MACE non-inferiority

9400 subjects will be enrolled to cumulate the first MACE events experienced by 611 unique subjects. The study duration may vary depending on actual MACE event rate and duration of enrolment period.

Table 2 Total Study Duration Sensitivity for Varying MACE Event Rate and Duration of Recruitment

| MACE rate (% pa) | Duration of recruitment | | | |
|------------------|-------------------------|---------|---------|---------|
| | 1.5 yrs | 2.0 yrs | 2.5 yrs | 3.0 yrs |
| 2.0 | 4.1yrs | 4.4yrs | 4.6yrs | 4.9yrs |
| 2.5 | 3.4 yrs | 3.7yrs | 3.9yrs | 4.2yrs |
| 3.0 | 3.0yrs | 3.2yrs | 3.5yrs | 3.8yrs |
| 3.5 | 2.7yrs | 2.9yrs | 3.2yrs | 3.4yrs |

